#### 6.2. KEY DEFINITIONS

Age

Age at screening is entered by site and this value will be used in all analyses.

Body Mass Index (BMI)

The BMI of a patient will be calculated in kg/m^2: BMI = body weight [kg] / (height [m])

Absolute Change from Baseline

Absolute change from baseline: Absolute change = Post-baseline value – Value at baseline

Relative change from baseline:

#### Statistical Analysis Plan

Version Final 2.0

Relative change = [(Post-baseline value – Value at baseline)/ Value at baseline] x100

#### Definition of Baseline

Baseline will be defined as the last available value before the first infusion of study medication and may be any visit between screening and day 1 (including the baseline visit [V2]) and unscheduled visit.

Duration of concomitant antibiotic treatment

If medication starts before date of first infusion (Visit 2, Day 1): Duration of concomitant antibiotic treatment [days] = Date of stop of antibiotic treatment – Date of first infusion +1.

If medication starts at/after date of first infusion (Visit 2, Day 1):

Duration of concomitant antibiotic treatment [days] = Date of stop of antibiotic treatment – Date of start of antibiotic treatment + 1

Duration of infusional AE

Duration of AE [hours] = (Date/time of stop of AE – Date/time of start of AE)

Duration of noninfusional AE

Duration of AE [days] = Date of stop of AE – Date of start of AE + 1

#### Time to onset of AE since last infusion prior AE

- For infusional AE: Time to onset of AE [hours] = Date/time of start of AE Date/time of start of last infusion prior AE
- For non-infusional AE: Time to onset of AE [days] = Date/time of start of AE Date/time of start of last infusion prior AE

#### Time to onset of AE since the first infusion

Time to onset of AE [days] = Date of start of AE – Date of first infusion

#### Infusional AE

Adverse events temporally associated with the infusion are AEs occurring during intravenous administration or within 1, 24, and 72 hours after the end of infusion.

Start Day of previous/concomitant medication If medication starts before date of first infusion (Visit 2, Day 1):

Start Day of Medication = Date of start of medication – Date of first infusion

If medication starts at/after date of first infusion (Visit 2, Day 1): Start Day of Medication = Date of start of medication – Date of first infusion + 1 Incomplete start dates of medication will not be imputed. Start day of medication will be missing.

Day of Study Termination Day of study termination = Date of termination – Date of first infusion + 1

# Definition of Completion

A subject will be defined as "completed" if s/he completes the Follow-up period of the study. Termination at a different time point will be considered as discontinuation.

# PID Diagnosis

Time since diagnosis [months] = ((Date of Informed Consent – Date of diagnosis)+1)/30

# 6.3. MISSING DATA

All available data will be included in the analyses and will be summarized as far as possible. Unless otherwise specified, there will be no substitution of missing data, i.e., missing data will not be replaced; missing data will be handled as 'missing' in the statistical evaluation.

Incomplete/missing start and stop date/time for AEs/antibiotic treatments will be handled as follow:

Start date will be imputed

- Missing start day with the day of first drug administration within that month. If no drug was administered then with '01'.
- Missing start day and month with the 1st of January. If the AE/antibiotic treatment start year = year of the first drug administration then with the date of the first drug administration.
- Missing start year with the date of the first drug administration
- In case an Investigator comment is available, imputation will take this into account:
  - o AE started before the day of a drug administration: missing start day with '01'
  - AE started after the day of a drug administration: missing start day with one day after the day of drug administration
  - AE started at least 72 hours after the day of a drug administration: missing start day with four days after the day of drug administration

Stop date will be imputed

- Missing stop day with last day (28/29/30/31) of the month.
- Missing stop day and month with 31st of December.
- Missing stop year with the date of study termination.

- Incomplete AE stop dates will only be imputed in case of the AE is not ongoing.

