#### Missing start time of AE

In case, AE can be assumed as infusional AE (started on the date of infusion or within 72 hours after last infusion), time will be imputed as 00:00. If date of AE start = Date of infusion start, date/time of AE start will be assumed as the date/time of the infusion start.

In case an Investigator comment is available for the assumed infusional AE, imputation will take this into account:

- AE started before treatment: time will be imputed as 00:00
- AE started during treatment: time will be imputed as start time of infusion
- AE started after treatment: time will be imputed as one minute after end of infusion

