#### Missing stop time of AE:

In case, AE can be assumed as infusional AE (started on the date of infusion or within 72 hours after last infusion, missing stop time will be imputed with end of day: 23:59

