#### 8.2.4. Time to Resolution of Infections

Time to resolution of infections (days) will be calculated as infection stop date – infection start date + 1. For the imputation rules of incomplete start/stop dates refer to Section 6.3. The presentation will include the continuous variable and also by categorizing the number of days until the resolution of infection the data according to the following categories:

- 1 to <3
- 3 to <5
- 5 to <8
- 8 to <10
- 10 to <14
- ≥14

Time to resolution will be presented for any infections, serious infections and nonserious infections.

Kaplan-Meier plots will be generated for time to resolution of infection by infusion schedule and overall.

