#### Infusional AEs:

Separate overall summaries of the infusional AEs will show the number and percentage of subjects who report during infusion or within 1, 24 or 72 hours after the end of infusion

- any infusional AEs,
- any serious infusional AEs,
- any nonserious infusional AEs,
- any related infusional AEs,
- any related infusional AEs by infusion,
- any serious related infusional AEs
- any infusional AEs by maximum severity
- any infusional AEs by infusion

The number and percentage of infusions temporally associated with 1 or more AEs that began during an infusion or up to 72 hours after the completion of the infusion will be displayed. This summary will be repeated for infusional ADRs.

The number and percentage of infusional AEs and of subjects with infusional AEs at each infusion (e.g. 1st infusion, 2nd infusion) will be presented for each infusion schedule. The mean number of AEs temporally associated with infusions per infusion will be calculated by (a)/(b) where: (a) equals the total number of AEs that occur during or within 72 hours of an infusion, and (b) equals the total number of infusions.

An exploratory upper 1-sided 95% exact confidence limit will be calculated for the proportion of the infusions with 1 or more infusional AEs (including nonproduct related). The proportion will be calculated as the total number of infusions with infusional AEs (AEs occurring during or within 1, 24, and 72 hours after the end of an infusion) divided by the total number of infusions. The upper 95% CI limit should be less than 0.4 to meet the FDA recommendation (FDA Guideline for industry 2008).

The number and percentage of subjects with AEs that occur during an infusion will be summarized by the infusion rate at which the AEs are reported. Further parameters will be time to onset (for infusional AEs), action taken, duration, outcome, severity, seriousness, and investigator causality.

In addition, the number and percentage of subjects with AEs occurring during infusion or within 1, 24 and 72 hours after infusion completion will also be summarized by SOC and preferred term. The same summary will be repeated for product related events (ADRs).

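### SAP 6.3 can impute a start date after the recorded stop date, giving zero or negative durations and tying an AE to an infusion given after it ended

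*SAP*

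**What the plan says.** SAP 6.3 opens its date rules with "Incomplete/missing start and stop date/time for AEs/antibiotic treatments will be handled as follow". A "Missing start day with the day of first drug administration within that month" is the default, with the first of the month used only where no infusion was given in that month. Where day and month are missing and the year is that of first dosing, or where the year is missing, the start becomes the date of first dosing.

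There is one override: "In case an Investigator comment is available, imputation will take this into account". A comment that the AE began before an infusion day moves the start to the first of the month. The listed comment cases speak of AEs, not of antibiotics.

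For missing times, SAP 6.3 states: "If date of AE start = Date of infusion start, date/time of AE start will be assumed as the date/time of the infusion start". For AEs assumed to be infusional, "missing stop time will be imputed with end of day: 23:59".

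These dates are then used in three places:

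- **Infections (SAP 8.2.4).** "Time to resolution of infections (days) will be calculated as infection stop date" minus start date plus 1, with reference to 6.3 for incomplete dates.
- **Antibiotics (SAP 6.2 and 8.2.5).** Stop minus start plus 1, with the days summed per subject and converted to monthly and annual rates.
- **Infusional AEs (SAP 6.2 and 11.3).** Status depends on onset. The proportion of infusions counts "AEs that began during an infusion or up to 72 hours after the completion of the infusion", and its upper one-sided 95% limit is set against 0.4.

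**The concern.** Assigning an ambiguous onset to the infusion is a reasonable worst-case convention for safety. It stops being reasonable when the recorded stop date shows that the event was over before the infusion began. Nothing in SAP 6.3 makes the programmer look at that date, and none of the duration formulas has a lower bound.

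Two errors follow. A duration of zero or less enters time to resolution and days on antibiotics. The resolution categories in SAP 8.2.4 start at 1 day, so such a value fits none of them, and a negative time cannot be used in the planned Kaplan-Meier plots. A negative antibiotic duration subtracts days from the subject's total.

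Secondly, an AE can be attributed to an infusion that came after it. It then counts in the proportion compared with 0.4 and in the FDA-specified adverse reaction table of SAP 11.3, where infusional timing alone qualifies an event. In the month of first dosing, a pre-treatment AE can become treatment-emergent.

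**Working it through.** The plan states no figure that depends on this rule, so there is none to reproduce. The check applies the rules literally and then counts how often they conflict with a recorded stop.

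**Worked dates.** The start is recorded only as May, the infusion is on 20 May, and there is no investigator comment. The infusion is assumed to begin at 09:00, and both AE times are missing. The imputed start is 20 May 09:00 and the imputed stop time is 23:59.

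| Recorded stop | Days (stop - start + 1) | Hours (infusional AE) |
|---|---|---|
| 5 May | 5 - 20 + 1 = -14 | -(14 × 24 + 9) = -345 |
| 19 May | 19 - 20 + 1 = 0 | -9 |
| 20 May | 20 - 20 + 1 = +1 | +15 |

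Hours are rounded to the nearest hour. In the first two rows the event ended before the infusion but is treated as starting at it. With a start of 1 May, the first row would give 5 - 1 + 1 = 5 days.

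**When the conflict can arise under the missing-day rule.** The stop day must be recorded and lie in the same month as the start. A missing stop day is set to month end, and a stop in a later month always follows the imputed start.

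**How often, given such a record.** Assumptions, none of them from the documents: a 30-day month; first infusion of the month uniform on days 1 to T, with T = 21 (3-week) or 28 (4-week); true duration D days; start day uniform over those that keep the stop within the month.

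- All combinations: T × (31 - D).
- Combinations with the stop before the infusion day: (T - D)(T - D + 1)/2.

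| D (days) | 3-week | 4-week |
|---|---|---|
| 3 | 171/588 = 0.29 | 325/784 = 0.41 |
| 7 | 105/504 = 0.21 | 231/672 = 0.34 |
| 10 | 66/441 = 0.15 | 171/588 = 0.29 |

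If the stop may fall in the next month, the denominator becomes T × 30. The shares are then 0.27, 0.17 and 0.10 (3-week) and 0.39, 0.28 and 0.20 (4-week).

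**Weight of one false infusional AE.** The visit schedule gives 14 infusions (4-week) or 18 (3-week) per completer. With 50 to 70 completers that is 50 × 14 = 700 to 70 × 18 = 1,260 infusions. One false event moves the proportion by at most 1/1,260 = 0.08 to 1/700 = 0.14 percentage points. Five move it by at most 0.4 to 0.7 points.

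**The other two start-date rules.** When day and month, or the year, are missing, the imputed start can be the date of first dosing, later than a stop recorded before it. For an AE this creates a false treatment-emergent event. For antibiotics the effect is limited, because SAP 7.5.1 treats a medication stopped before the first infusion as previous.

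**The case against.** The strongest reply is that few records should be affected, and that SAP 6.3 already deals with some of them. The investigator-comment override gives the first of the month, which is the sensible answer. The protocol also works to obtain onset dates: the investigator confirms infection onset and diaries are kept in real time (9.1.2.1), subjects are contacted 1, 24 and 72 hours after each infusion (9.2.1.2), onset date is an eCRF item for every AE (9.3.2), and validation checks and queries follow (11.2). All of this stands. It narrows the gap to AEs without a comment and to antibiotic records, but a recorded stop date alone still triggers nothing.

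A reader might infer that 15-41% of all AEs or antibiotic courses are misdated. The documents do not support that: the percentages are conditional on a record type whose frequency is not given.

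A reader might also infer that the rule threatens the efficacy claim or helps the product pass the 0.4 comparison. Neither follows. The primary endpoint counts events, with onset on the day of diagnosis (SAP 8.1.1), so these durations do not enter it. False infusional events raise the proportion, which works against the product, and the limit is labelled exploratory.

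**Conclusion.** The gap is real but small. Followed literally, SAP 6.3 gives impossible durations and can attribute an AE to an infusion that began after the AE had ended. This applies to AEs without a clarifying investigator comment and to antibiotic records. False infusional or treatment-emergent status concerns AEs only. A stop one day before the infusion gives a day-based duration of 0 rather than a negative one.

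Among records with the start day missing, start and stop in one month and no comment, about 15-29% (3-week) and 29-41% (4-week) would be affected for events of 10 down to 3 days. This rests on the uniform-day assumptions above. The documents do not allow a count of such records, so no effect on an endpoint can be stated.

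The two errors differ in direction: the exploratory infusional proportion is inflated, while resolution times and antibiotic days are shortened. The latter are descriptive secondary summaries. The primary analysis and sample size do not depend on the rule.

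**What to change.** Add to SAP 6.3, for all three start-date rules (missing day; missing day and month; missing year) and for both AEs and antibiotics:

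1. No imputed start may fall after a known stop date. If it would, use the earliest date compatible with the recorded part of the start date, such as the first of the month, or the stop date where no such date precedes it.
2. An AE is not classed as infusional for an infusion that began after the AE's recorded stop.
3. Infusional status that rests only on an imputed start date is flagged in the listings.

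The third item is needed because the first of the month can itself fall within 72 hours of the preceding infusion. On a 3-week schedule, the infusion before 20 May is due on 29 April, and an AE start imputed as 1 May at 00:00 is within its window. The stop date should not be made conditional on the event having lasted one day, since that cannot be known when the start is missing.

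The cost is a few sentences in 6.3, a line in the infusional AE definition and one listing flag. No new data are needed, and sample size is unchanged. Stating the rule in advance also avoids choosing a repair after the records have been seen.

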#### 8.2.2. Rate of Any Infections

Infections are identified by the following criteria:

- Any AE leading to the MedDRA SOC "infections and infestation".
- All AEs leading to any other SOC are reviewed by the sponsor for possible relation to an infection (e.g. pyrexia leading to SOC General disorders and administration site conditions). Identified AEs possibly related to this endpoint are queried to the investigator. The investigator transfers his decision to the eCRF (AE term).

The annual rate of infections will be calculated as the mean number of all infections (serious plus nonserious) per subject-year as described in Section 8.1.1. The annual rate per subject will be the total number of infections of the subject divided by the total duration expressed in years of the observation period of the subject. Summaries will be as for a continuous variable and by categorizing the number of any infections per subject according to the following categories:

- 0
- 1
- 2
- 3 to <5
- 5 to <10
- ≥10

The annual rate of days with infections per subject will be the total number of days with infections of the subject divided by the total duration expressed in years of the observation period of the subject.

Frequency tables presenting the number (%) of subjects with infections, the number of days with any infections and the total number of infections will be done.

Tables will also be stratified by season (spring, summer, autumn, winter) using the calendar whereas e.g. spring starts on 01Mar.

In addition, summaries will be done for the subgroup of subjects that did not receive treatment for the full period of time, either by missing an infusion or discontinuing the study.

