#### 8.2.5. Antibiotic Treatment Information

Monthly rates of days on concomitant antibiotic treatment will be calculated per subject-month. The monthly rate per subject will be the total number of days on antibiotics of the subject divided by the total duration expressed in months (of 30 days) of the observation period of the subject. For the imputation rules of incomplete start/stop dates refer to Section 6.3. Summaries will be as for a continuous variable.

Annual rates of days on concomitant antibiotic treatment will be calculated per subject-year. The annual rate per subject will be the total number of days on antibiotics of the subject divided by the total duration expressed in years (of 365 days) of the observation period of the subject. For the imputation rules of incomplete start/stop dates refer to Section 6.23.

Summaries will be as for a continuous variable and also by categorizing the number of days on antibiotic treatment according to the following categories:

- 0
- >0 to <7
- 7 to <14
- 14 to <21
- 21 to <35
- 35 to <70
- >=70

Summaries will be done for the number of subjects requiring treatment with antibiotics and the number of days on antibiotic treatment.

In addition, the number and percentage of subjects taking concomitant antibiotic medications will be summarized by ATC Levels 2, 3 and 4.

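### Antibiotic-day and infection-day rates can count days after the last visit, because neither the stop-date imputation nor the day count is bounded there

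*SAP*

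**What the plan says.** SAP 6.3 opens its date rules with "Incomplete/missing start and stop date/time for AEs/antibiotic treatments will be handled as follow". Infections are recorded as adverse events, so they are covered along with antibiotics. There are three stop-date rules:

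- day missing: "Missing stop day with last day (28/29/30/31) of the month";
- day and month missing: "Missing stop day and month with 31st of December";
- year missing: "Missing stop year with the date of study termination".

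Only the third is tied to the end of the subject's participation. One restriction follows, for adverse events only: "Incomplete AE stop dates will only be imputed in case of the AE is not ongoing".

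SAP 6.2 defines antibiotic duration. When treatment began before the first infusion, the count starts at that infusion: "Duration of concomitant antibiotic treatment [days] = Date of stop of antibiotic treatment – Date of first infusion +1". Nothing in 6.2 limits the count at the other end.

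These days feed rates over the subject's observation period. SAP 8.2.2 states "The annual rate of days with infections per subject will be the total number of days with infections of the subject", divided by that period in years; 8.2.3 does the same for nonserious infections. SAP 8.2.5 treats days on antibiotics likewise, per month and per year, and sends the reader back to 6.3: "For the imputation rules of incomplete start/stop dates refer to" that section. SAP 8.1.1 defines each subject's duration as running from first infusion to last visit, both days included. I found no upper limit on counted days or imputed stop dates elsewhere in the protocol or SAP.

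**The concern.** A rate of days per subject-year is coherent only if every counted day lies in the time that forms the denominator. Here the denominator closes at the last visit, while the numerator can run to the end of that month or year. Such a subject's rate is overstated.

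The imputation rules also sit oddly together. With the stop year unknown, the stop becomes the date of study termination. With the year known, it becomes 31 December, which may be months later. Knowing more yields a less plausible date.

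At stake are the descriptive summaries of antibiotic days and of days with any or nonserious infections, including the day categories in 8.2.5. The SAP summarises per-subject rates as a continuous variable, so one extreme record can move a mean noticeably.

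**Working it through.** The plan states no figure on this point, so there is none to reproduce. The check applies the SAP formulas to assumed dates.

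**Inputs from the documents.** Stop-date rules: SAP 6.3. Duration: SAP 8.1.1. Planned last visit: Day 379 (3-week) or Day 393 (4-week), from the flowchart in SAP 3.8. About 70 subjects enrolled, at least 50 evaluable: SAP 3.5.

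**Assumed.** All calendar dates below, and one affected record per example.

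**Formulas.** Counted days D = stop − start + 1. Observed days T = last visit − first infusion + 1. Annual rate = D / (T/365). Overrun E = imputed stop − last visit, when positive. Days inside follow-up = D − E.

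**Step 1: largest possible overrun.** Overrun requires the partial stop date to lie in the month (day missing) or year (day and month missing) of the last visit.
- Day missing, last visit on the 1st of a 31-day month: 31 − 1 = 30 days.
- Day and month missing, last visit on 1 January of a 365-day year: 365 − 1 = 364 days. If last visits were spread evenly over the year, the mean would be (0 + 364)/2 = 182 days.

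**Step 2: one hypothetical record.** Last visit 15 March (day 74 of the year), year-only stop: E = 365 − 74 = 291 days. Shared over 70 subjects, 291/70 = 4.2 days. As an annual rate, 291/(379/365)/70 = 4.0 or 291/(393/365)/70 = 3.9, so about 4 days/year.

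**Step 3: three assumed records, with and without a limit at the last visit.**

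| Record | T | Days, as written / limited | Days per year, as written / limited | Shift in mean, n=70 / n=50 |
|---|---|---|---|---|
| A. 4-week completer: first infusion 1 Feb 2018, last visit 28 Feb 2019, start 10 Feb 2019, stop year 2019 only | 393 | 325 / 19 | 301.8 / 17.6 | 4.1 / 5.7 |
| B. 4-week completer: first infusion 5 Feb 2018, last visit 4 Mar 2019, start 1 Mar 2019, stop month March 2019 | 393 | 31 / 4 | 28.8 / 3.7 | 0.4 / 0.5 |
| C. Early dropout: first infusion 15 Jan 2018, last visit 12 Feb 2018, start 1 Feb 2018, stop year 2018 only | 29 | 334 / 12 | 4,204 / 151 | 58 / 81 |

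If A is an antibiotic course, it moves from the 14 to <21 days category of 8.2.5 to the top one, ≥70.

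**Step 4: when does a rate pass 365 days/year?** When D exceeds T. Record C does (334 > 29); record A does not (325 < 393). A completer with the 15 March overrun would need more than 379 − 291 = 88 or 393 − 291 = 102 days of the same course inside follow-up. At the 364-day extreme those thresholds fall to 15 and 29 days.

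**Step 5: effect of averaging per subject.** Protocol 10.6 pooled antibiotic days over all subjects; SAP 13.1.6 replaces this with per-subject rates. Record C has 334 − 12 = 322 excess days. Pooled over an assumed 70 subject-years they add 322/70 = 4.6 days/year; averaged per subject they add (4,204 − 151)/70 = 58.

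**The case against.** The case for leaving the plan alone has four parts.

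- **The triggers are narrow.** A completer's planned follow-up exceeds 365 days and so crosses a year end; a year-only stop in the earlier year does not overrun. Protocol Appendix 1 requires an end date for every resolved adverse event, and diaries are reviewed every 3 or 4 weeks. A resolved infection with only a year recorded should be rare. This stands, and it limits the likely size.
- **Ongoing infections are not imputed.** This also stands. A reader might infer that every unresolved infection is pushed to 31 December; the restriction in 6.3 rules that out. The restriction names only adverse events, so exposure is wider for antibiotics.
- **The error counts against the product.** This is true, and 6.3 also takes the worst case for missing severity, seriousness and causality. But a worst-case rule should not give impossible values, and the missing-year rule does not follow that logic.
- **Nothing confirmatory depends on it.** This stands. The primary endpoint counts events and uses no stop dates.

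A reader might also infer that time to resolution (8.2.4) has the same fault. The documents do not support that. It is stop minus start plus 1, with no observation-period denominator, and Protocol 9.3.4 provides for following serious, severe or related events past the last visit, so a true resolution can come later. Forcing the stop back to the last visit could record resolution while the infection was still present.

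**Conclusion.** The concern holds for the antibiotic-day and infection-day rates. As written, the plan can count days outside the period it divides by: up to 30 per record with only the day missing, up to 364 with day and month missing. The 291 days and roughly 4 days/year on a 70-subject mean describe one hypothetical record. The documents do not say how many stop dates are incomplete, so the realised effect could be nil.

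A reader might take rates above 365 days/year to be a general risk. Among the records worked here, only the dropout with short follow-up produces one; a short course in the completer does not.

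Imputation is not the only route. A fully recorded stop date after the last visit causes the same mismatch, because 6.2 does not trim the stop. The remedy therefore belongs mainly in how days are counted. This is a minor point about descriptive secondary outputs, and the primary analysis is untouched.

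**What to change.** 1. In SAP 6.2, 8.2.2, 8.2.3 and 8.2.5, state that antibiotic and infection days enter the rates only from first infusion to last visit inclusive, whether the stop date is recorded, imputed or ongoing.
2. In SAP 6.3, for these day rates, take the earlier of the imputed stop date and the last visit, and never a date before the start.
3. In SAP 8.2.4, do not use that limit as a resolution date. Censor infections not known to have resolved by the last visit.

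The cost is a few sentences and a small programming change, with no new data. If the analysis has already been run, the same counting rule can be applied and reported as a documented change, with the number of incomplete stop dates alongside so that the effect can be judged.
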